4.2.3 Handling of missing data for prior and concomitant medication

A complete start and stop date must be established to correctly identify the medication as prior or concomitant. For purposes of imputing missing components of partially reported start and stop dates for medications, the algorithms listed below will be followed. Start and stop dates of medications will be displayed as reported in the subject data listings (i.e. no imputed values will be displayed in data listings).

Partial start dates for medications which started during AS0008 and were ongoing at the start of AS0009 will be taken from the AS0008 database based on the dedicated eCRF page for imported medications in AS0009

Imputation of all partial start dates for medications (including those reported on the ‘imported’ page) will follow the rules below (treatment switching rules refer to AS0008 only):

- If only the month and year of the medication start date are specified, and the month and year of the start date of study medication in AS0009 are not the same as the month and year of the medication start date, and the subject did not switch treatment during that month and year, then use the 1st of the month of the medication start date.
- If only the month and year of the medication start date are specified, and the month and year of the start date of study medication in AS0009 are not the same as the month and year of the medication start date, and the subject switched treatment during the month and year of the medication start date, then use the date of treatment switch.
- If only the month and year of the medication start date are specified, and the month and year of the start date of study medication in AS0009 are the same as the month and year of the medication start date, then use the start date of study medication in AS0009 (regardless of treatment switching). If this results in a start date after a known end date use the 1st of the month of the medication start date.
- If only the year of the medication start date is specified, and the year of start date of study medication in AS0009 is not the same as the year of the medication start date, and the subject did not switch treatment during the year of the medication start date, then use the 1st of January of the year of the medication start date.
- If only the year of the medication start date is specified, and the year of the start date of study medication in AS0009 is not the same as the year of the medication start date, and the subject switched treatment during the year of the medication start date, then use the date of treatment switch.
- If only the year of the medication start date is specified, and the year of the start date of study medication in AS0009 is the same as the year of the medication start date, then use the start date of study medication in AS0009 (regardless of treatment switching). If this results in a

start date after a known end date use the 1st of January of the year of the medication start date.

- If only the year and day of the medication start date are specified, and the year of the start date of study medication in AS0009 is not the same as the year of the medication start date, then use January of the year of the medication start date together with the known day.
- If only the year and day of the medication start date are specified, and the year of the start date of study medication in AS0009 is the same as the year of the medication start date, then use the start month of study medication in AS0009 together with the known day.
 - If this results in a start date after a known end date use January of the year of the medication start date together with the known day.
 - If this results in a start date prior to the start date of study medication in AS0009 (in the imputed month) the medication will be considered to be concomitant.
- If the medication start date is completely unknown and the medication stop date is unknown or not prior to the start date of study medication in AS0009, then use the start date of study medication in AS0009.

Imputation of partial medication stop dates:

- If only the month and year of the medication stop date are specified, then use the last day of that month and that year.
- If only the day and year are specified, then use December of that year
- If only the year of the medication stop date is specified, then use December 31st of that year.
- If the medication stop date is completely unknown, do not impute the stop date.

In the event of ambiguity or incomplete data which makes it impossible to determine whether the medication was prior or concomitant, the medication will be considered concomitant. For subjects who may have died during the study, imputed dates will be truncated at the date of death.

There will be no imputation of any other missing data for concomitant medications.

4.2.4 Handling of partial treatment end dates

The date of last study drug administration in AS0009 may be completely unknown (e.g., if the subject is lost to follow-up) or partially known. In the latter case, it is possible to enter a known month and year into the database but to leave the day as missing (i.e., YYY-MMM-XX) on the study termination page of the CRF.

Missing or partial treatment end dates will be handled according to the following rules:

- For subjects for whom the treatment end date is completely missing on the study termination page, the date of last dose in AS0009 will be the date/time of the last known dose as reported on the study medication administration page of the CRF.

- For any subjects who terminated the study in AS0009 without receiving a dose of study medication, the treatment end date will be the last date of last study drug administration in AS0008.
- For subjects for whom the treatment end date is partially missing (i.e., only the month and year are known) the following rules will be applied:
 - The treatment end date will be imputed as date of last known study medication administration + 28 days (i.e., equivalent to the dosing interval), assuming this gives an imputed date in the known month and year
 - If the above rule results in an imputed date that is not in the known month and year the following will apply:
 - If the date of last known study medication +28 days results in a month PRIOR to the month of the partial date, then the imputed date of last dose will be set to the 1st of the known month i.e., YYYY-MMM-01.
 - If the date of last known study medication +28 days results in a month AFTER the month of the partial date, then the imputed date of last dose will be set to the last day of the known month e.g., YYYY-MM-31 (modified according to the calendar month).

In the listings the date of last study drug administration will be displayed as received in the data i.e., without imputation.

4.3 Interim analyses and data monitoring

An interim analysis will be performed after the final subject has reached AS0009 Week 108, based on two years' exposure in the study. All outputs described in this SAP will be presented with the exception of COVID-19 related tables and listings. The datasets for the interim analysis will include all data collected up to this point; the 'by-visit' summaries will present data only up to the Week 108 time point; summaries of AEs and exposure will present all data collected up to the time of the database cut-off date (ie, when the final subject has reached AS0009 Week 108).

Additional data cuts may also be performed for regulatory and publication purposes.

4.4 Multicenter studies

The data from all centers will be pooled for the purposes of the analysis. There will be no formal statistical evaluation of the effect of center on the results obtained.

Centers will be grouped into the geographic regions of North America, Western Europe and Eastern Europe as described in [Section 3.8](#) for use as a covariate in statistical analyses and for sub-group analyses.

4.5 Multiple comparisons/multiplicity

Not applicable.

4.6 Use of an efficacy subset of subjects

Not applicable.

4.7 Active-control studies intended to show equivalence

Not applicable.

4.8 Examination of subgroups

Subgroup analyses will be performed for the following secondary efficacy variables:

- ASAS20, ASAS40 and ASAS5/6 response at AS0009 Week 48.
- Change from Baseline in BASDAI at AS0009 Week 48.

The following variables for subgroup analyses will be used:

- Geographic region at AS0008 Baseline (North America, Western Europe and Eastern Europe)
- Previous (past) TNF inhibitor exposure at AS0008 Baseline (yes, no). The value in the AS0008 database for past anti-TNF therapy (as collected on the eCRF) will be used for AS0009, without additional derivation.
- Concomitant NSAID status at start of AS0008 (yes, no). The value in the AS0008 database for past NSAID therapy (as collected on the eCRF) will be used for AS0009, without additional derivation.

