3.10 Changes to protocol-defined analyses

The following changes have been made to the protocol-defined analyses:

- Change from AS0009 EV for safety variables will no longer be presented, since the EV assessment is made after 36 or 48 weeks of bimekizumab treatment and there is unlikely to be any further important change.
- Change from AS0008 Baseline and AS0009 EV for laboratory variables will not be presented, due to a change in laboratory vendor between AS0008 and AS0009. Laboratory Baseline has been defined as the earliest value in AS0009 at or prior to AS0009 Week 12.
- Summaries of ASAS40, ASAS20 and ASAS5/6 response at each post-AS0008 Baseline visit have been added for subjects who were responders at AS0008 Week 12. These summaries include all post-AS0008 Baseline visits through to AS0009 Week 208, for subjects in the FAS for AS0009, and will be used to assess maintenance of response.
- The protocol describes the FAS as consisting of all enrolled subjects who receive at least 1 dose of IMP and have a valid measurement for at least 1 efficacy variable at AS0009 study entry. This has been updated to include all subjects in the ES who received at least one dose of study medication in AS0009 and have a valid measurement for at least one efficacy variable at a scheduled visit (excluding SFU visits) after AS0009 EV. This was updated in order to identify subjects who have had assessments during AS0009 and which contribute to any of the efficacy analyses.
- Summaries by randomized treatment in AS0008 will not be produced, as subjects will have been on a constant dose of bimekizumab 160mg or 320mg for at least 36 weeks prior to AS0009 entry. Maintenance of response displays will be split by treatment sequence across AS0008 and AS0009. Safety displays using AS0008 information will incorporate exposure in AS0008.
- The protocol defines subgroups based on ‘Concomitant non-steroidal anti-inflammatory drug (NSAID) status at AS0009 entry. This has been updated to ‘Concomitant NSAID status at start of AS0008’.
- The protocol stated that all safety analysis would be performed for both Sub-populations; instead only key safety analyses will be repeated by Sub-population as identified in [Section 10](#). These analyses will be performed only in the event that the number of subjects receiving rescue medication is $\geq 10\%$ of the total number of subjects in the SS.

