6.2 Other baseline characteristics

AS history including the time since first diagnosis of AS (at time of enrolment in AS0008 and at time of enrolment in AS0009), time since first symptoms of AS (at time of enrolment in AS0008 and at time of enrolment in AS0009), age at first diagnosis date, and AS subtype (clinical criterion a, b, c or radiologic criterion) will be summarized by treatment group at completion of AS0008 and overall for the SS.

Time since first diagnosis will be summarized as a continuous variable and as categorical variable. Time since first diagnosis of AS at time of enrolment in AS0008 will be taken from the AS0008 database. Time since first diagnosis of AS at time of enrolment in AS0009 will be calculated as below, where date of diagnosis will be taken from the AS0008 database:

Time since first diagnosis

$$\begin{aligned} &= \text{Date of informed consent in AS0009} \\ &\quad - \text{Date of first diagnosis in AS0008} \end{aligned} \quad (9)$$

Time since first diagnosis for each study will be categorized as: < 5 , ≥ 5 years.

Time since first symptoms of AS at time of enrolment in AS0008 will be taken from the AS0008 database. Time since first symptoms at time of enrolment in AS0009 will be calculated as:

$$\begin{aligned} & \text{Time since first symptom} \\ & = \text{Date of informed consent in AS0009} \quad (10) \\ & \quad - \text{Date of first symptom in AS0008} \end{aligned}$$

Age at first diagnosis will be taken from the AS0008 database. AS history will be listed for the ES.

The following baseline characteristics will be summarized by treatment group at the completion of AS0008 and overall for SS:

- BASDAI total score.
- BASDAI spinal pain (Question 2).
- PGADA.
- Total spinal pain (Question 1 of the TNSP questionnaire).
- BASFI.
- ASDAS-CRP.
- CRP.
- HLA-B27 (positive, negative).
- Anti-TNF therapy prior to first dose in AS0008 (yes, no). The value in the AS0008 database for past anti-TNF therapy (as collected on the eCRF) will be used for AS0009, without additional derivation.
- NSAID therapy prior to first dose to first dose in AS0008 (yes, no). The value in the AS0008 database for past NSAID therapy (as collected on the eCRF) will be used for AS0009, without additional derivation.
- Current number of NSAID therapies (0, 1, 2, ≥ 3).
- Current synthetic disease modifying anti-rheumatic drugs (DMARDs) (methotrexate [MTX], sulfasalazine, hydroxychloroquine) (yes, no).
- Current corticosteroid use (yes, no)

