One summary table will be produced for AS0008 Baseline values and another for AS0009 EV values. NSAID, HLA-B27 and anti-TNF therapy prior to first dose will be based on data collected in AS0008 and will be included in the AS0008 Baseline table only.

BASDAI, BASDAI spinal pain (Q2), PGADA, total spinal pain (Q1 of the TNSP questionnaire), BASFI, ASDAS-CRP, CRP, current NSAID, current synthetic DMARDs and current corticosteroids will be included in both tables. CRP values at AS0009 EV will be taken from the Week 48 record in the AS0008 database. For the summary of AS0009 EV data, current NSAID, current synthetic DMARD and current corticosteroid therapy are defined as medications that are

ongoing at the AS0009 EV, or that started on the date of the AS0009 EV. This does not include medications that were stopped on the date of the AS0009 EV. In addition, for AS0009, current corticosteroid therapy will include oral medications only.

Baseline characteristics, including AS0008 Baseline and AS0009 EV values for the repeated variables, will be listed for the ES.

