6.4 Past, prior and concomitant medications

Only medications that were ongoing at the end of AS0008 or were started during AS0009 will be reported.

Concomitant medications are medications taken at least 1 day in common with the study medication dosing period in AS0009 (as defined in [Section 3.2.2](#)). A medication is classed as concomitant if the start date is no later than the end date of study medication in AS0009 + 28 days, and the stop date is either missing or on or after the start date of study medication in AS0009. This includes medications that started prior to dosing in AS0009 and continued after.

For the purposes of the analysis, past medications are medications that started and stopped prior to dosing in AS0008. These include past TNF therapy (for subgroup analyses, MI modelling and baseline characteristics) and past NSAID therapy (for Baseline characteristics).

Missing or partial medication start and stop dates will be imputed as described in [Section 4.2.3](#). Imputations of missing data will be performed before calculation of relative study days and classification as concomitant.

The number and percentage of subjects taking concomitant medications will be summarized by ATC class, presenting Anatomical Main Group (ATC Level 1), Pharmacological Subgroup (ATC level 3), and PT, by treatment group at completion of AS0008 and overall for the SS.

All medications reported in AS0009, including flags to identify concomitant and rescue medications, and start and stop days relative to the start date of study medication in AS0008 and start and stop days relative to the start of study medication in AS0009, will be listed for the ES.

A glossary of all medications including the Anatomical Main Group (ATC Level 1), Pharmacological Subgroup (ATC level 3) PT and reported term will also be presented, based on the ES.

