6.5 Prohibited medication and rescue therapy

The following medication categories will be identified:

- Rescue medications as defined below. Subjects in the category ‘Any concomitant rescue therapy in AS0009’ will be considered SS Sub-population 2 and other subjects will be considered SS Sub-population 1. Rescue medications will be identified using the flag collected in the eCRF.
- NSAIDs to identify subgroups/covariates.
- Prohibited medications.

Rescue medications and NSAIDs will be classified into subcategories for reporting purposes. The identification and classification of concomitant medications will be performed by merging an external physician-reviewed spreadsheet (which includes relevant flags for selecting medications in each category) with the data entered into the study database in order to categorize the medications correctly for the tables.

The number and percentage of subjects who receive the following categories of rescue medication will be summarized by treatment group at completion of AS0008 and overall for the SS.

- Any rescue medication in AS0009 that is classified as a concomitant medication as defined in [Section 6.4](#).
- NSAID at AS0009 EV
- No NSAID at AS0009 EV
 - No NSAID at AS0009 EV and initiate NSAID [but not Cox-2 inhibitors] in AS0009 (only the initiation of NSAIDs that are classified as concomitant medications as defined in [Section 6.4](#) will be included).
 - No NSAID at AS0009 EV and initiate Cox-2 inhibitors in AS0009 (only the initiation of Cox-2 inhibitors that are classified as concomitant medications as defined in [Section 6.4](#) will be included).
- Use of any DMARDs in AS0009 alone or in combination (includes MTX, sulfasalazine, leflunomide and hydroxychloroquine). Only concomitant medications will be included as defined in [Section 6.4](#).
- Intra-articular corticosteroid in AS0009 that is classified as concomitant as defined in [Section 6.4](#).
- Oral corticosteroid in AS0009 that is classified as concomitant as defined in [Section 6.4](#).

- Analgesics in AS0009 that are classified as concomitant as defined in [Section 6.4](#).

Rescue therapy category and medication name, start date and day relative to start of study medication in AS0008 and AS0009 will be listed for the SS.

PRN analgesic and PRN opioid analgesic use within 24 hours prior to study visits will be listed for the ES, based on the dedicated eCRF page for prohibited medications.

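### The concomitant NSAID subgroup in SAP 4.8 is filled from a past-NSAID field, which does not give concomitant status on either description in the SAP

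*SAP*

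**What the plan says.** Protocol 13.4.1 lists concomitant NSAID status at AS0009 entry as a subgroup variable. SAP 3.10 records a change to "Concomitant NSAID status at start of AS0008", so the time point moves and the word concomitant stays.

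SAP 4.8 gives the working definition: "Concomitant NSAID status at start of AS0008 (yes, no). The value in the AS0008 database for past NSAID therapy", as collected on the eCRF, carried into AS0009 with no further derivation. SAP 8.4 refers to 4.8 for all subgroup definitions and applies them to ASAS20, ASAS40, ASAS5/6 and BASDAI change at AS0009 Week 48 in the FAS.

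Four other statements bear on that field:

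- SAP 6.2 uses it, with the same sourcing sentence, for "NSAID therapy prior to first dose to first dose in AS0008 (yes, no".
- SAP 6.2 lists "Current number of NSAID therapies" as a separate item and says that "current NSAID, current synthetic DMARDs and current corticosteroids will be included in both tables", that is, the AS0008 Baseline and AS0009 EV tables.
- SAP 6.4 states that "past medications are medications that started and stopped prior to dosing in AS0008". It names subgroup analysis among the uses of past TNF therapy, but for NSAIDs it mentions only "past NSAID therapy (for Baseline characteristics").
- SAP 6.5 lists "NSAIDs to identify subgroups/covariates" among the medication categories to be identified, with classification through a physician-reviewed spreadsheet.

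**The concern.** Within one bullet of SAP 4.8, the label describes use at a point in time and the source describes earlier use. The sourcing sentence repeats the one in the TNF bullet above it with the drug class changed. There it fits, because previous TNF inhibitor exposure is a history variable; for a concomitant variable it does not.

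A programmer following 4.8 would split subjects by NSAID history and head the tables concomitant NSAID. A reader could then draw a conclusion about background NSAID use from a split that does not measure it, and the question in Protocol 13.4.1 would go unanswered. If the field means any NSAID before first dose, the no group would contain only subjects with no NSAID before AS0008 dosing, and it could be too small to interpret.

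**Working it through.** The plan gives no figure to reproduce, so the check sets the definitions side by side by subject type. Concomitant status is taken as NSAID use at the first AS0008 dose.

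| Subject's NSAID use | Concomitant at start of AS0008 | Field as described in 6.4 (started and stopped before dosing) | Field as described in 6.2 (before first dose) |
|---|---|---|---|
| Started earlier, still ongoing | yes | no | yes |
| Stopped before AS0008 dosing | no | yes | yes |
| Never used | no | no | no |
| Started on the day of first dose | yes | no | no |

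Each row assumes a single course. The 6.4 description is wrong in three of the four rows and the 6.2 description in two. No other section reconciles them: SAP 3.10 declares only the time-point change, and the definition of concomitant in 6.4 concerns the AS0009 dosing period, so the past-therapy field is the only operational rule for this subgroup.

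To show how large the error could be, let p be the share with a past, stopped NSAID and c the share with a current NSAID. **Neither is in the documents; all values below are assumptions.** A subject may have both.

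- 6.4 description, misclassified share if independent: p(1−c) + (1−p)c. With any dependence: |p−c| to min(p+c, 2−p−c).
- 6.2 description, misclassified share if independent: p(1−c). With any dependence: max(0, p−c) to min(p, 1−c). This leaves out starts on the day of first dose.
- No group out of the enrolment ceiling of 285 (Protocol 13.10): true non-users 285(1−c); under 6.2 with independence 285(1−p)(1−c).

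| Assumed (p, c) | 6.4, independent | 6.4, range | 6.2, independent | 6.2, range | True no group | No group under 6.2 |
|---|---|---|---|---|---|---|
| (0.95, 0.90) | 0.095 + 0.045 = 14% | 5–15% | 9.5% | 5–10% | 28.5 | 1.4 |
| (0.85, 0.70) | 0.255 + 0.105 = 36% | 15–45% | 25.5% | 15–30% | 85.5 | 12.8 |
| (0.50, 0.80) | 0.10 + 0.40 = 50% | 30–70% | 10% | 0–20% | 57.0 | 28.5 |

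Reach: SAP 4.1 lists region and past TNF inhibitor exposure as the imputation covariates and does not list NSAID status, so the error does not enter the multiple imputation.

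**The case against.** The strongest objection is that the AS0008 eCRF is not available. The field may in fact capture ongoing users, and the word past may simply have been carried over from the TNF bullet. The 6.4 definition is stated for analysis purposes, whereas 4.8 takes a collected value unchanged, so the 6.2 description may be the closer one, and it overlaps with concomitant status. This stands as a limit on what can be said about actual misclassification. It does not rescue the text, because 6.2 still counts subjects who had stopped and still treats current use as a separate variable.

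The figures also rest on assumed p and c, and the counts use the enrolment ceiling rather than the FAS. Both points are correct: the table shows possible size and is not evidence of actual size.

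The spreadsheet route in 6.5 may be partly residual. SAP Amendment 1 dropped concomitant NSAID status from the imputation model, which could explain the mention of covariates, and 8.4 makes 4.8 govern. So 6.5 is better seen as text needing alignment than as a firm rival rule. That 4.8 governs makes its wording matter more.

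Finally, the impact is modest: one of three descriptive subgroup factors, at one visit, in a single-arm extension with a safety objective. That is accepted.

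**Conclusion.** The concern holds. The label and source in SAP 4.8 disagree, and neither of the SAP's own descriptions of the source field yields concomitant NSAID status at the start of AS0008. This follows from the wording and does not depend on the missing eCRF. The share of subjects actually misclassified does depend on it and cannot be determined; the illustrative figures span 0% to 70% across both descriptions and any dependence.

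As written, the NSAID subgroup summaries for ASAS20, ASAS40, ASAS5/6 and BASDAI at Week 48 would carry a heading that their data do not support. The primary safety results, the overall secondary efficacy results and the imputation models are unchanged. This should be corrected, but it does not threaten the study's main conclusions.

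**What to change.** In SAP 4.8, replace the sourcing sentence of the NSAID bullet with a rule such as: yes if the current number of NSAID therapies at AS0008 Baseline (Section 6.2) is 1 or more, no if 0. State what current means at AS0008 Baseline, because 6.2 spells this out only for the AS0009 EV.

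Two alternatives are acceptable:

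- Return to the protocol's AS0009-entry status, for which 6.2 already has the rule and 6.5 the categories. This would reverse the change declared in 3.10.
- If NSAID history is what is wanted, rename the subgroup accordingly and declare the switch in 3.10.

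Whichever is chosen, align 4.8, 6.4 and 6.5 on one source. SAP 4.3 plans all outputs except the COVID-19 ones at the Week 108 interim, and the Amendment 2 rationale refers to a review of interim results, so the correction should be recorded openly as a change.

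The cost is one sentence in 4.8, a short rule for current use, and consistency edits in 6.4 and 6.5. No new data are needed, since current NSAID use is already planned for both baseline tables. Any NSAID subgroup tables already produced under the present rule would need re-running.
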